13.1.2 EQ VAS Score

The EQ VAS score at baseline and each of the post-HSCT assessments will be summarized and presented using descriptive statistics. A higher EQ VAS score represents better QoL. For each of the post-HSCT assessments, change between baseline and that assessment in the EQ VAS score will be calculated and will be summarized and presented using descriptive statistics.

$$\text{Change in the EQ VAS} = [\text{EQ VAS at the post-HSCT assessment}] - [\text{EQ VAS at baseline}]$$

The following summary will be provided:

- Summary of EQ-5D-5L VAS score for adult subjects (age ≥ 16 years)

13.2 EQ-5D-Y

13.2.1 EQ-5D-Y Dimension

For each of the 5 dimensions based on the descriptive system of the EQ-5D-Y, self-report version, the numbers and percentages of subjects for all categories (the 3 levels of reported problems and question not completed) at baseline and each of the post-HSCT assessments will be presented. For each subject at a specific post-HSCT assessment, change between baseline and that assessment in each dimension will be categorized similarly to the change in each of the five dimensions in EQ-5D-5L (Section [13.1.1](#)). The numbers and percentages of subjects for all categories in change between baseline and each of the post-HSCT assessments will be presented for each dimension.

The following summaries will be provided:

- Summary of EQ-5D-Y dimensions for pediatric subjects (age ≥ 8 and ≤ 15 years) by assessment
- Summary of change in EQ-5D-Y dimensions from baseline for pediatric subjects (age ≥ 8 and ≤ 15 years) by assessment
-

The following listing will be provided and will include results for each of the 5 dimensions and the VAS score:

- Listing of EQ-5D-Y

13.2.2 EQ VAS Score

The EQ VAS score at baseline and each of the post-HSCT assessments will be summarized and presented using descriptive statistics. For each of the post-HSCT assessments, change between baseline and that assessment in the EQ VAS score will be calculated as mentioned in Section [13.1.2](#) for a specified subject, and will be summarized and presented using descriptive statistics.

The following summary will be provided:

- Summary of EQ VAS score for pediatric subjects (age ≥ 8 and ≤ 15 years)

13.3 EQ-5D-Y Proxy Version 1

13.3.1 EQ-5D-Y Proxy Version 1 Dimension

For each of the 5 dimensions based on the descriptive system of the EQ-5D-Y, self-report version, the numbers and percentages of subjects for all categories (the three levels of reported problems and question not completed) at baseline and each of the post-HSCT assessments will be presented. For each subject at a specific post-HSCT assessment, change between baseline and that assessment in each dimension will be categorized similarly to the change in each of the 5 dimensions in EQ-5D-5L (Section [13.1.1](#)). The numbers and percentages of subjects for all categories in change between baseline and each of the post-HSCT assessments will be presented for each dimension.

The following summaries will be provided:

- Summary of EQ-5D-Y dimensions for pediatric subjects (age ≥ 4 and ≤ 7 years) by assessment
- Summary of change in EQ-5D-Y dimensions from baseline for pediatric subjects (age ≥ 4 and ≤ 7 years) by assessment

The following listing will be provided and will include results for each of the 5 dimensions and the VAS score:

- Listing of EQ-5D-Y Proxy Version 1

13.3.2 EQ VAS Score

The EQ VAS score at baseline and each of the post-HSCT assessments will be summarized and presented using descriptive statistics. For each of the post-HSCT assessments, change between baseline and that assessment in the EQ VAS score will be calculated as mentioned in Section [13.1.2](#) for a specified subject, and will be summarized and presented using descriptive statistics.

The following summary will be provided:

- Summary of EQ VAS score for pediatric subjects (age ≥ 4 and ≤ 7 years)

14 BIOMARKERS

Biomarker analysis is not within the scope of this SAP and a separate report will be provided for the analysis of biomarkers.

15 IMMUNOGENICITY

Immunogenicity analysis is not within the scope of this SAP and a separate report will be provided for the analysis.

16 PHARMACOKINETIC ANALYSES

16.1 General Considerations

Pharmacokinetic (PK) analysis for this study will be conducted in 2 separate efforts. For those subjects with intensive PK sampling scheme and those who developed VOD and received defibrotide rescue treatment, a noncompartmental analysis will be conducted and reported in this CSR. The PK sample collection schedule in subjects who developed VOD and received defibrotide rescue treatment underwent several changes across protocol amendments. The results of this analysis will be produced and summarized by day and time points as covered by the protocol version which was current at the time of PK sample collection, and as outlined in Sections [16.2](#) and [16.3](#). For those subjects with sparse PK sampling scheme, a population-based PK analysis will be conducted together with PK data from other studies. The population PK will be reported separately from the CSR.

Quantitative variables will be summarized using descriptive statistics (sample size, arithmetic mean, SD, coefficient of variation, median, min, and max). Geometric statistics (mean and SD) will be included for PK concentrations and parameters, where applicable.

All defibrotide concentration data will be reported and analyzed with the same precision as the source data provided by the bioanalytical laboratory regardless of how many significant figures or decimals the data carry. Derived PK parameters will be rounded for reporting purposes in listings. The rounded derived PK parameters will be considered the source data for the calculation of descriptive statistics and other statistical analysis. For most derived PK parameters, 3 significant digits will be used as the standard rounding procedure, with the following exceptions:

- Parameters directly derived from source data (eg, maximum defibrotide concentration [C_{max}]) will be reported and analyzed with the same precision as the source data.
- Parameters derived from actual elapsed sample collection times (eg, time to maximum activity [T_{max}]) will be reported with the same precision as the actual elapsed sampling time value of the source data.

For the reporting of descriptive statistics, the arithmetic and geometric means and SDs will be presented with precision of 1 digit more than the source data. The minimum, median, and maximum will be presented with the same precision as the source data. Coefficients of variation will always be reported with 1 decimal place.

16.2 Defibrotide Plasma Concentrations

The defibrotide plasma concentrations will be summarized by nominal time point using descriptive statistics as described in [Section 16.1](#). Concentrations that are below the limit of quantitation (BLQ) will be treated as a numeric value of 0, and the associated geometric statistics will be designated and reported as not done.

The following summaries will be provided:

- Summary of defibrotide plasma concentrations in subjects consented for intensive PK collection

- On Day +1 and Day +7 post-HSCT: prior to defibrotide infusion, and 2, 2.25, 2.5, 2.75, 3, 3.5, 4 and 5 hours after start of defibrotide infusion;
- On Day +15 and Day +30 post-HSCT: 2 hours post start of defibrotide infusion;
- Summary of defibrotide plasma concentrations in subjects with sparse PK sampling
 - On Day +7 post-HSCT: 2 hours post start of defibrotide infusion, 2 to 4 hours after the end of defibrotide infusion;
 - On Day +15 and Day +30 post-HSCT: 2 hours post start of defibrotide infusion;
- Summary of defibrotide plasma concentrations in subjects who developed VOD and received defibrotide rescue treatment by treatment arm (BSC or DP)
 - On Day 1 after the start of rescue treatment: prior to defibrotide infusion, and 2, 3, 4 and 5 hours after start of defibrotide infusion (Protocol Amendment 3);
 - On Day 7 after the start of rescue treatment: 2 hours post start of defibrotide infusion (Protocol Amendment 3);
 - On Day 14 after the start of rescue treatment: prior to defibrotide infusion, at 2 hours post start of defibrotide infusion, and at 1, 2 and 3 hours after end of defibrotide infusion (Original Protocol), or prior to defibrotide infusion, and 2, 3, 4 and 5 hours after start of defibrotide infusion (Protocol Amendments 1&2)
 - On Day 30 after the start of rescue treatment: 2 hours post start of defibrotide infusion (Original Protocol, and Protocol Amendments 1&2);

Figures of individual and arithmetic mean defibrotide concentration-time profiles (\pm SD, as appropriate) using nominal time points in patients consented to intensive PK collection on Day +1 and Day +7 post-HSCT and in patients receiving defibrotide rescue treatment on Day 1 and Day 14 after the start of rescue treatment, will be presented on linear and semi-logarithmic scales. For graphing purposes, the BLQ values will be considered as missing and, if applicable, 2 neighboring values will be connected.

The following figures will be provided:

- Mean Defibrotide Plasma Concentration-time Profile on Linear and Semi-logarithmic Scales following Defibrotide Infusion at 6.25 mg/kg on Day +1 post-HSCT
- Mean Defibrotide Plasma Concentration-time Profile on Linear and Semi-logarithmic Scales following Defibrotide Infusion at 6.25 mg/kg on Day +7 post-HSCT
- Mean Defibrotide Plasma Concentration-time Profile on Linear and Semi-logarithmic Scales following Defibrotide Infusion at 6.25 mg/kg after the start of rescue treatment in Patients from DP Arm by Visit
- Mean Defibrotide Plasma Concentration-time Profile on Linear and Semi-logarithmic Scales following Defibrotide Infusion at 6.25 mg/kg after the start of rescue treatment in Patients from BSC Arm by Visit

A listing of all defibrotide plasma concentrations by subject, with visit (day), study arm, PK blood sample collection date/time, calculated actual collection times relative to the previous dose, and derived sampling time deviations will be provided:

- Listing of defibrotide plasma concentrations

16.3 Defibrotide Pharmacokinetic Parameters

Subjects with partial defibrotide concentrations data, protocol violations or events with the potential to affect PK will be evaluated on a case-by-case basis to determine if sufficient data are available for reliable estimation of PK parameters.

PK parameters will be calculated for the patients consented for intensive PK collection on Day +1 and Day +7 post-HSCT; and for patients who developed VOD and received defibrotide for rescue treatment on Day 1 (Protocol Amendment 3) and on Day 14 (Original Protocol, and Protocol Amendments 1&2) after the start of rescue treatment, as data permit.

The defibrotide plasma PK parameters will be calculated using the standard noncompartmental analysis methods according to current working practices and Phoenix WinNonlin (Certara USA, Inc., v6.3 or higher).

All calculations of noncompartmental parameters will be based on actual sampling times for the analysis, but all predose times will be assigned a numerical value of 0 to prevent overestimation of the AUC.

Defibrotide plasma concentrations that are BLQ or missing will be handled the following way:

- Predose samples concentrations that are BLQ or missing will be assigned a numerical value of 0.
- Any other BLQ value will be assigned a value of 0 if they precede quantifiable samples in the initial portion of the profile.
- A BLQ value that occurs between quantifiable data points, especially prior to C_{max} , will be evaluated to determine if an assigned value of 0 makes sense, or if exclusion of the data (flagged in the data and identified to be treated as missing) is warranted.
- Following C_{max} , the BLQ values embedded between 2 quantifiable data points will be treated as missing when calculating PK parameters.
- If a BLQ value occurs at the end of the collection interval (after the last quantifiable activity), it will be set to 0.
- If consecutive BLQ values are followed by quantifiable values in the terminal portion of the concentration curve, these quantifiable values will be excluded from the PK analysis by setting them to missing, unless otherwise warranted by the concentration-time profile.

Where possible the following PK parameters listed in Table 6 will be determined from defibrotide plasma concentrations.

Table 6. PK Parameters to be Summarized

C_{max}	Maximum defibrotide plasma concentration, obtained directly from the observed data
T_{max}	Time of maximum defibrotide concentration (in hours), obtained directly from the observed data
C_{last}	The last quantifiable defibrotide concentration, obtained directly from observed data
T_{last}	Time of the last quantifiable defibrotide concentration (in hours), obtained directly from the observed data
AUC_{0-t}	Area under the defibrotide concentration-time curve in the sampled matrix from 0 (predose) to time of last quantifiable defibrotide concentration at time “t”
AUC_{tau}	Area under the defibrotide plasma concentration-time curve from 0 (predose) to the end of the dosing period (Day +7 post-HSCT and Days 1 and 14 after the start of rescue treatment in patients from DP arm)
AUC_{0-inf}	Area under the defibrotide plasma concentration-time curve from 0 (predose), extrapolated to infinity by addition of the last quantifiable concentration divided by the elimination rate constant to AUC_{0-t} : $AUC_{0-t} + C_{last} / \lambda_z$ (Day +1 post-HSCT and Day 1 after the start of rescue treatment in patients from BSC arm)
λ_z (k_{el})	Apparent terminal elimination rate constant (in 1/hour), determined by linear regression of the terminal points of the log-linear defibrotide concentration-time curve Visual assessment will be used to identify the terminal linear phase of the defibrotide concentration-time profile. A minimum of 3 data points will be used for the determination.
$t_{1/2}$	Terminal elimination half-life (in hours): $\ln(2) / \lambda_z$
CL	Systemic clearance after intravenous dosing, calculated as 
 • Dose/AUC_{0-inf} (Day +1 post-HSCT and Day 1 after the start of rescue treatment in patients from BSC arm) • Dose/AUC_{tau} (Day +7 post-HSCT and Days 1 and 14 after the start of rescue treatment in patients from DP arm)
V_{ss}	Estimate of the volume of distribution at steady state following intravenous dosing: $MRT_{0-inf} \times CL$, where MRT_{0-inf} is mean residence time extrapolated to infinity

All AUC parameters will be calculated using Linear trapezoidal / Linear Interpolation trapezoidal summation. The minimum requirement for the calculation of AUC will be the

inclusion of at least 3 consecutive plasma concentrations above the lower limit of quantification, with at least 1 of these concentrations following C_{max} .

The PK parameters listed in Table 7 will be calculated for diagnostic or parameter derivation purposes and listed, but will not be summarized.

Table 7. PK Parameters for Diagnostic or Parameter Derivation Purposes

Span	The time spanned by λ_z (upper λ_z – lower λ_z) divided by the estimated $t_{1/2}$. The $t_{1/2}$ will be estimated over a time period of at least 2 half-lives, where possible. Where a $t_{1/2}$ is estimated over a time period of less than 2 half-lives, it may be flagged in the data listings at the discretion of the Pharmacokineticist, and the robustness of the value will be discussed in the CSR.
$t_{1/2}$, N	Number of data points included in the log-linear regression analysis to determine λ_z A minimum of 3 data points will be used for determination.
Rsqr, adjusted	Goodness of fit statistic for calculation of λ_z A value of ≥ 0.8 for the adjusted R-squared value will be used as the criterion for the reliable estimation of λ_z and reporting of the $t_{1/2}$. If the adjusted R-squared value does not meet this criterion for a given subject the $t_{1/2}$, AUC_{0-inf} , CL, and V_{ss} will be listed but not included in the descriptive statistics.
%AUC _{extr}	Percentage of AUC_{0-inf} obtained by extrapolation: $[(C_{last} / \lambda_z) / AUC_{0-inf} \times 100]$ If %AUC _{extr} is greater than 20% of AUC_{0-inf} , then AUC_{0-inf} , CL, and V_{ss} will be listed but not included in summary statistics.
AUMC _{last}	Area under the first moment curve (AUMC) from 0 (pre-dose) to time of last quantifiable defibrotide concentration at time “t”
AUMC _{0-inf}	Area under the first moment curve (AUMC) extrapolated to infinity, based on the last observed concentration, calculated as $AUMC_{last} + (T_{last} \times C_{last}) / \lambda_z + C_{last} / \lambda_z$
MRT _{0-inf}	Mean residence time extrapolated to infinity, calculated for infusion models as $(AUMC_{0-inf} / AUC_{0-inf} - TI) / 2$, where TI is infusion time

All PK parameters will be summarized by visit and study arm using descriptive statistics as described in Section [16.1](#). Geometric mean will not be calculated for T_{max} and T_{last} .

The following summaries will be provided:

- Defibrotide plasma pharmacokinetic parameters following defibrotide infusion at 6.25 mg/kg on Day +1 post-HSCT

- Defibrotide plasma pharmacokinetic parameters following defibrotide infusion at 6.25 mg/kg on Day +7 post-HSCT
- Defibrotide plasma pharmacokinetic parameters following defibrotide infusion at 6.25 mg/kg after the start of rescue treatment by Visit.

The following listing will be provided and will include all generated individual PK parameters by subject, visit (day), and treatment arm:

- Listing of PK parameters

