DESIGN	
This is a Phase 3, randomized, adaptive study comparing the efficacy and safety of defibrotide vs BSC in the prevention of hepatic VOD in adult and pediatric patients undergoing HSCT who are at high risk or very high risk of developing VOD, as diagnosed using the modified Seattle criteria. A total of 400 patients are planned for enrollment to ensure completion of approximately 360 patients. An interim analysis overseen by an independent Data Monitoring Committee (DMC) is planned when 70% of patients are evaluable for the primary efficacy endpoint (i.e., VOD-free survival by Day +30 post-HSCT), with pre-specified rules for efficacy stop, futility stop, and possible sample size re-estimation up to a maximum of 600 patients total. After informed consent or assent has been obtained from patients, or legal parent/guardians or representatives, as applicable, screening procedures will be performed within 14 days of the scheduled start of the patient's HSCT conditioning regimen. Eligible patients will be randomly assigned to receive defibrotide prophylaxis 25 mg/kg/day in addition to BSC ("DP arm") or BSC alone ("BSC arm") in a 1:1 ratio. Randomization will be stratified according to risk of developing VOD (high-risk or very high-risk), age (>16 years or ≤16 years), and country using an interactive web response system (IWRS). Enrollment of those patients meeting high-risk criteria will be capped at 65% of the total enrollment using IWRS.
 
All patients enrolled in the study will receive individualized standard of care therapy based on local institutional guidelines and patient need. This standard of care therapy or "best supportive care" (BSC) is intended to serve as a study control for comparison with those patients randomized to receive defibrotide prophylaxis. Patients randomized to the "best supportive care" arm (BSC arm) will receive standard of care therapy per institutional guidelines and patient need; patients randomized to the defibrotide prophylaxis arm (DP arm) will also receive standard of care therapy based on local institutional guidelines and patient need plus defibrotide prophylaxis. Prophylactic use of defibrotide added to "best supportive care" (DP arm) will be compared to "best supportive care" (BSC arm).
 
Administration of defibrotide to patients in the DP arm will begin within 24 hours of the first dose of conditioning regimen (i.e., Study Day 1), and will continue (for those patients without a VOD diagnosis) for a recommended minimum of 21 days and end no later than Day +30 post-HSCT. (Note: 21 days of defibrotide prophylaxis corresponds to approximately Day +15 post-HSCT, assuming 5 days of conditioning therapy prior to HSCT). For patients in the BSC arm, administration of BSC according to institutional

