### 1.3 Justification for Dosage and Dosage Regimen

The dosage of defibrotide selected for this study is 25 mg/kg/day, administered intravenously as 4 2-hour infusions of 6.25 mg/kg every 6 hours beginning the day before the first day of the conditioning regimen for a recommended minimum of 21 days and stopping no later than Day +30 post-HSCT. Each dose (infused over a 2 hour  $\pm$ 15 min infusion period) may be administered within  $\pm$ 1 hour of the scheduled dosing time provided that there is at least a 2-hour window between the end of an infusion and the start of the next infusion. Using a consistent minimum duration of inpatient treatment in the DP arm is seen as necessary for accurate assessment of a treatment effect. Although VOD is typically diagnosed before Day +21 post-HSCT (Bearman 1995, Richardson and Guinan 1999), 21 days of prophylactic treatment (corresponding to approximately Day +15 post-HSCT, assuming 5 days of conditioning therapy prior to HSCT) was selected in order to allow an optimal time for diagnosis of VOD while minimizing patients’ exposure to the unnecessary risks of prolonged hospitalization should a patient be ready for early hospital discharge. Discharge of patients from the hospital before they have received the recommended minimum duration of treatment (i.e., 21 days) will not constitute a protocol violation as this does not impact efficacy or safety analyses.

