#### 5.2.1.1 Defibrotide Prophylaxis

For patients randomized to receive defibrotide prophylaxis, 2-4 doses of defibrotide should be administered within 24 hours before the first dose of conditioning regimen. Defibrotide administration is recommended for a minimum of 21 days and ending no later than Day +30 post-HSCT. Patients in this arm of the study will also receive standard of care therapy based on institutional guidelines and patient need (i.e., BSC). Patients must undergo Day +15 post-HSCT assessments before hospital discharge. If a patient is discontinued early from study/study treatment (prior to Day +15 post-HSCT), the Day +15 post-HSCT assessments must be completed on the day of study/study treatment discontinuation (+1 day).

If a patient on defibrotide develops bleeding, defibrotide should be discontinued. Additionally, temporary discontinuation of defibrotide is recommended for patients at significant risk of major bleeding who are receiving defibrotide (prophylactically or as rescue medication) and who undergo surgery or invasive procedures (see [Section 1.6.1](#)).

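### Day +1 post-HSCT clearance uses a single-dose formula in patients already dosed every 6 hours, so it is understated and not comparable with Day +7 (descriptive PK only)

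*SAP*

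**What the plan says.** Table 6 in SAP section 16.3 has two clearance rules:

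- Dose/AUC0-inf applies to "Day +1 post-HSCT and Day 1 after the start of rescue treatment in patients from BSC arm".
- Dose/AUCtau applies to "Day +7 post-HSCT and Days 1 and 14 after the start of rescue treatment in patients from DP arm".

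The AUC0-inf and AUCtau rows are split the same way.

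The same section sets times as well as concentrations. For times, "all predose times will be assigned a numerical value of 0 to prevent overestimation of the AUC". For concentrations, "Predose samples concentrations that are BLQ or missing will be assigned a numerical value of 0". The concentration rule makes no distinction between a first dose and a later one. SAP section 16.2, on concentration summaries, sets only BLQ values to zero and does not mention missing ones.

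On dosing history, Protocol section 1.3 has DP dosing "beginning the day before the first day of the conditioning regimen for a recommended minimum of 21 days", and section 5.2.1.1 says "2-4 doses of defibrotide should be administered within 24 hours before the first dose of conditioning regimen". Section 5.2.1 gives 2-hour infusions every 6 hours. Section 6.6.2.1 places the Day +1 profile at the first infusion of that day starting after 6:00 AM.

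**The concern.** Dose/AUC0-inf equals clearance when nothing is on board before the sampled dose. On a multiple-dose profile the tail beyond 6 hours contains drug from earlier infusions as well. The whole of it is credited to one dose, and clearance comes out too low. At steady state the correct quantity is Dose/AUCtau.

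The SAP applies that reasoning elsewhere. It separates DP from BSC patients on rescue Day 1, and the evident reason is that DP patients have already been dosed. The same reason applies to DP patients on Day +1 post-HSCT, yet they are grouped with BSC patients starting rescue.

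At stake is a secondary objective, characterizing the pharmacokinetics, in an intensive-sampling group of about 25 patients (Protocol section 6.6.2). Day +1 and Day +7 parameters get separate tables that readers will compare. Because the formula changes between them, a patient whose clearance is constant appears to have higher clearance on Day +7.

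The zero rule raises a smaller question of the same kind. In a patient dosed every 6 hours, a missing predose sample is an unmeasured trough, not a zero.

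**Working it through.** **Dosing history.** The protocol's own timeline comes first: 21 days of dosing is "corresponding to approximately Day +15 post-HSCT, assuming 5 days of conditioning therapy prior to HSCT". Study Day 1 is the day before conditioning, conditioning fills Study Days 2 to 6, and HSCT (Day 0) is Study Day 7. Day +15 is then Study Day 22, so 21 full days end as Day +15 begins. The stated figure is reproduced. Doses before Day +1 are 2 to 4 before conditioning, 5 × 4 = 20 during conditioning and 4 on the HSCT day: about 26 to 28.

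**Inputs.** Infusion 2 h, interval 6 h, last sample 5 h after the start of infusion (Protocol sections 5.2.1 and 6.6.2.1). AUC by the linear trapezoid (SAP 16.3). The half-life h is not in the documents, so it is an assumption shown over a range. The model is one-compartment at steady state, with k = ln2/h.

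**Clearance on Day +1.** At steady state AUCtau = Dose/CL and AUC0-inf = AUCtau + C(6)/k. Let

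r = C(6)/(k·AUCtau) = (1 − e^(−2k))·e^(−4k) / [2k·(1 − e^(−6k))].

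Then Dose/AUC0-inf = CL/(1 + r), an understatement of r/(1 + r). For h = 1 h: r = 0.75 × 0.0625 / (1.386 × 0.9844) = 0.0343, so CL is understated by 3.3%. For a true first dose, Dose/AUC0-inf returns CL exactly.

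**Missing predose set to 0.** In units of the end-of-infusion concentration the trough is x = 2^(−4/h). The first trapezoid (0 to 2 h) loses x, and AUCtau is about 1 + x + (h/ln2)(1 − x). For h = 1 h: x = 0.0625, AUCtau = 2.415, and the loss is 2.6%.

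| Assumed half-life | Day +1 CL understated by | AUC0-inf extrapolated beyond 5 h | AUCtau lowered if predose missing |
|---|---|---|---|
| 0.5 h | 0.1% | 0.5% | 0.2% |
| 1 h | 3.3% | 6.6% | 2.6% |
| 1.5 h | 9.9% | 15.7% | 5.3% |
| 1.7 h | 12.8% | 19.2% | 6.2% |
| 2 h | 17.1% | 24.2% | 7.3% |

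**The 20% rule.** SAP Table 7 takes AUC0-inf, CL and Vss out of the summaries when more than 20% of AUC0-inf is extrapolated. With the SAP's sampling times and trapezoid that point is reached at a half-life of about 1.7 h. The largest error left in summarized CL is therefore about 13%.

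**Both rules together.** A zeroed predose raises CL while AUC0-inf lowers it. On Day +1 at h = 1.5 h, AUC0-inf from the SAP's sampling times is about 1.113 × AUCtau. Removing 0.053 leaves 1.060, and 1/1.060 gives a net CL error of about −6% instead of −10%. On Day +7 only the zero rule can act. It overstates CL by about 0.2%, 2.6% and 5.6% at 0.5, 1 and 1.5 h, which widens the gap from Day +1.

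**The case against.** The case for leaving this alone has real substance.

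- **Size.** It rests on a half-life that the documents do not state. Table 7 aims to estimate half-life over at least two half-lives where possible. Within the 2 to 5 h sampling window that means 3/2 = 1.5 h or less, which suggests that the planners expected short values. At 0.5 h both errors are negligible. This stands, and it is why only a range can be given.
- **Safeguards.** The 20% rule keeps the larger errors out of the summaries. That stands, but it removes the slower-eliminating patients and does not correct the formula. Section 16.3 also sends partial profiles to case-by-case review. That review decides whether the data suffice; it does not replace the zero rule.
- **Use.** No test or estimate of change from Day +1 to Day +7 is planned. Protocol section 9.11 also provides a population PK analysis of all samples, which would not use these formulas, although SAP section 16.1 describes it for sparse-sampling patients.

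A reader might infer that the SAP treats DP multiple-dose profiles in general as first doses. It does not: Day +7 and DP-arm rescue Days 1 and 14 already use AUCtau, so the clearance formula is wrong for one visit. A reader might also take the 17% at 2 h as the error in the reported summaries. In this model such a profile exceeds the 20% limit and appears in listings only. Nor is the zero rule a general bias: it matters only when a predose sample is missing, and zero for a true BLQ value is a minor approximation.

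**Conclusion.** The Day +1 clearance rule is wrong as written, and it conflicts with the SAP's own handling of Day +7 and of DP-arm rescue Day 1. Day +1 CL is understated by about 0.1%, 3%, 10% and 13% at assumed half-lives of 0.5, 1, 1.5 and 1.7 h, with 13% about the ceiling for summarized values. The zero rule for a missing predose sample is a lesser fault: about 0.2% to 6% of AUCtau over the same range, conditional on the sample being missing, and in the opposite direction for CL.

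The direction follows from the algebra. The sizes rest on a one-compartment steady-state model and the assumed half-lives. They isolate the two rules from a separate limit of the schedule: with no sample between 0 and 2 h, the linear trapezoid itself overstates CL by about 4% at 1.5 h and 22% at 0.5 h. That error enters both visits, so it does not explain a difference between them.

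This is a minor point. It concerns descriptive PK and bears on no efficacy conclusion.

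**What to change.** 1. In Table 6, move Day +1 post-HSCT from the AUC0-inf and Dose/AUC0-inf rows to the AUCtau and Dose/AUCtau rows. The last sample is at 5 h, so AUCtau needs extension to 6 h, as it already does on Day +7.
2. Limit the zero rule for missing predose samples to profiles that dosing records confirm as the patient's first defibrotide dose. Otherwise use the concentration extrapolated to 6 h, or leave AUC and CL missing.
3. For BSC rescue Day 1, choose the single-dose or multiple-dose rule according to whether the sampled infusion was the first. Protocol section 6.6.2.3 lets the samples come from any one dosing interval that day, so a first dose cannot be assumed.

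The cost is a few SAP lines and minor reprogramming. No new data are needed.
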